Statistical Analysis Plan PACSPI 2

TRIAL FULL TITLE	Patient-controlled Sedation in Port Implantation (PACSPI_2) - a randomized controlled trial
EPM Nr	EPM: 2022-00088-01
EPM amendment Nr	EPM: 2022-00088-02
EUDRACT NUMBER	2021-003821-31
SAP VERSION	1.0
STUDY CODE	Futurum-963747
SAP VERSION DATE	2022-03-17
TRIAL STATISTICIAN	[name]
TRIAL SPONSOR	[name]
TRIAL PRINCIPAL INVESTIGATOR	[name]
SAP AUTHOR	[name]

1 SAP Signatures

I give my approval for the attached SAP entitled **Patient-Controlled Sedation in Port Implantation (PACSPI-2) -a randomized controlled trial** dated Monday, 3rd october 2022. I assure that this trial will be conducted in compliance with all stipulations of this statistical analysis plan, the conditions in the Swedish Ethical Review Authority and Swedish medical products agency approval, standards of Good Clinical Practice (defined by the International Conference on Harmonisation), ethical principles that have their origin in the Declaration of Helsinki and all applicable national and local regulations.

Trial Sponsor

Name: [name]

Signature: _____

Date: _____

Principal Investigator

Name: [name]

Signature: _____

Date: _____

Trial Steering Group

Trial Sponsor

[name]
OP/IVA kliniken
Ryhov County Hospital
[name]
Email: [contact]>

Principial Investigator

[name]
OP/IVA kliniken
Ryhov County Hospital
[name]
Email: [contact]>

Co-Investigator

[name]
An/OP/IVA kliniken
Linköping University Hospital
Email: [contact]>

Co-Investigator

[name]
An/OP/IVA kliniken
Linköping University Hospital
Email: [contact]>

Co-Investigator

[name]
An/OP/IVA kliniken
Linköping University Hospital
Email: [contact]>

Co-Investigator

[name]
OP/IVA kliniken
Ryhov County Hospital
[name]
Email: [contact]>

Statistician

[name]
Futurum
Ryhov County Hospital
[name]
Email: [contact]>

Monitor:

FORUM Östergötland
Region Östergötland
Universitetssjukhuset I Linköping
[name]
[contact]

Study Summary:

Title: Patient-Controlled Sedation in Port Implantation (PACSPI 2) – a randomized controlled trial.

Design: A randomized controlled trial at two centres with a total of 340 patients.

Aims: To determine if patient-controlled sedation (PCS) with propofol and alfentanil reduces patient-reported pain perception during implantation of subcutaneous venous port (SVP).

Outcome Measures: The primary outcome is pain perception. Secondary outcomes include patient satisfaction and efficacy measures such as periprocedural time consumption, sedation levels, insertion conditions as well as safety measures, adverse events and quality of recovery.

Population / Eligibility: Patients ≥ 18 years with cancer in need of SVP.

Exclusion criteria:

- Inability to operate the PCS apparatus.
- Inability to communicate in Scandinavian languages.
- Patients who require general anaesthesia or patients eligible for LA only on anesthesiologist's assessment (i.e. severe sleep apnea).
- Propofol or alfentanil allergy.
- Non-fasting according to guidelines of the Swedish Society for Anaesthesia and Intensive Care (SFAI).
- Failure to achieve peripheral vascular access.
- Pregnancy
- Previous participation in study

Trial medication: Propofol 10mg/ml, Alfentanil 0,5mg/ml. A syringe loaded with 36ml Propofol and 4ml Alfentanil in a patient controlled sedation (PCS) pump with 0.5ml aliquots per pressed handheld button.

Duration of Trial Participation: Participation in the trial will continue until the patient is discharged from the postoperative unit having completed the patient questionnaire. For measurement of quality of recovery a telephone interview will be performed one day postoperatively.

Study period: Q 4 2022-Q3 2024.

2 Table of Contents

1	SAP Signatures.....	1
2	Table of Contents.....	4
3	Abbreviations and Definitions.....	5
4	Introduction.....	7
4.1	Existing Research and pilot studies.....	8
4.2	Purpose of the analyses.....	8
4.3	Study Objectives.....	8
5	Study Methods.....	10
5.1	General Study Design and Plan.....	10
5.2	Method.....	11
5.3	Inclusion-Exclusion Criteria and General Study Population.....	12
5.4	Enrolment, Flow sheet, Randomization and Blinding.....	12
5.4.1	Enrolment.....	12
5.4.2	Randomization.....	13
5.5	Withdrawal Criteria.....	13
5.5.1	Blinding.....	13
5.6	Study Variables.....	14
6	General Considerations.....	19
6.1	Data requisition.....	19
6.2	Timing of Analyses.....	19
6.3	Analysis Populations.....	19
6.3.1	Full Analysis Population.....	19
6.3.2	Per Protocol Population.....	19
6.3.3	Intention to Treat Analysis.....	19
6.4	Subgroups.....	19
6.5	Missing Data.....	19
6.6	Interim Analyses and Data Monitoring.....	20
6.6.1	Interim Analyses and Data Quality.....	20

6.6.2	Stopping Rules	20
6.6.3	Bias	20
6.7	Multi-centre Studies	20
6.8	Multiple Testing	20
7	Summary of Study Data	21
7.1	Data collection	21

More than 60.000 patients are diagnosed with cancer every year in Sweden. Many of these patients are eligible for chemotherapy through a totally implanted venous access device (TIVAD) commonly referred to as a subcutaneous venous port (SVP). According to the Swedish Perioperative Register [1] the implantation of SVPs is one of the most common surgical procedures in Sweden. However there is no current guidance as to which procedural analgesic strategy is superior during SVP-implantation.

The implantation procedure can be performed in local anaesthesia (LA) only, LA in combination with analogosedation or under general anaesthesia. Practice is likely to be based on local institutional traditions rather than evidence-based guidance.

During SVP implantation using LA alone one fourth of patients experience severe pain and discomfort often leading to administration of sedatives and analgesics for pain relief [2].

Clinician-controlled sedation (CCS) involves administration of procedural analogosedation by a trained clinician. However, it carries the risk of oversedation and generates higher costs compared to alternative sedation methods [3, 4]. Patient-controlled sedation (PCS) is an alternative sedation method to CCS, enabling patients to self-administer and self-regulate their sedation and analgesia during the procedure. The procedural use of PCS with different sedatives and analgesics is well described and regarded as a safe alternative with a lower incidence of analgesic or sedative rescue interventions compared to CCS in a number of clinical settings [5]. Propofol and alfentanil, with their short-acting properties, ensure rapid induction and recovery, making them suitable for outpatient procedures.

The optimal procedural sedative and analgesic strategy regarding the care for patients in need of SVP-implantation is unclear and to the best of our knowledge no randomized controlled trial (RCT) has assessed PCS with propofol and alfentanil as adjunct to LA during SVP-implantation.

A patient's ability to resume normal activities after surgery and anaesthesia is an important indicator of a successful perioperative experience. Quality of recovery-15 (QoR-15) is a validated psychometric patient-centered outcome measure after day case surgery. QoR-15 has not been used in patients undergoing SVP implantation. This study will assess patients' perioperative experience by using QoR-15.

In this multicenter RCT we aim to examine the effect of PCS with propofol and alfentanil on patients' self-reported pain perception scores, overall satisfaction scores, sedation scores and incidence of adverse events.

4.1 Existing Research and pilot studies

Review of the literature

Searching for publications in the literature is challenging due to widespread terminology of TIVAD's. No less than ten different synonyms were identified (central venous port catheter; subcutaneous venous port; totally implantable access device; totally implantable venous access system; port-a-cath, totally implantable access port; long term central venous catheters, central venous access device, totally implantable subcutaneous port, subcutaneously implanted port-chamber catheter, implantable chest wall port). All synonyms are aiming at the same device- a subcutaneously buried device connected to a catheter with its tip in a large bore vein.

We conducted a review of the literature.

Pubmed was searched up to 10th March 2022 for randomized controlled trials.

We searched pubmed with the above mentioned synonyms AND patient-controlled sedation. 1 RCT with 40 patients was identified comparing effects between PCS and radiologist-controlled sedation (RCS) during tunnelled central line insertion [6]. The applied medication being midazolam and fentanyl in both PCS and RCS.

Search for the above mentioned synonyms AND sedation AND adults resulted in 8 studies of which 3 are designed as RCT's [6-8].

4.2 Purpose of the analyses

These analyses will assess the efficacy of patient-controlled sedation on reduction of patient-reported pain and distress during subcutaneous venous port insertion. It will measure patients' perioperative experience.

4.3 Study Objectives

The primary objective is to determine the efficacy of patient-controlled sedation (PCS) as adjunct to local anaesthesia (LA) on patients' self-reported pain perception during SVP-implantation. Patients in the treatment arm will undergo SVP insertion in LA combined with PCS and in the control arm SVP insertion will be conducted in LA.

The second objective is analyses of patient distress and satisfaction as well as secondary efficacy outcomes and determination of the relative safety of the treatment arm on defined safety outcomes and all adverse events and costs.

Primary endpoint: The primary endpoint is assessment of patient-reported pain perception. Endpoints are assessed by the use of the numeric rating scale (NRS):

- maximal intraprocedural pain level on NRS

Secondary endpoints:

- satisfaction with pain treatment during implantation
- maximal distress level
- importance of receiving sedatives during implantation
- overall satisfaction
- overall satisfaction with the staff
- maximal pain from arm with PCS infusion
- importance of being in control of sedation administration
- grading of implantation conditions by the implanting physician
- perioperative and procedural time consumption
- delivered doses of alfentanil and propofol
- rescue-therapy by nurse
- differences in cost
- vital parameters: oxygen saturation, heart rate, blood pressure
- sedation levels according to Observers Assessment of Alertness/Sedation scale (OAA/S)
- procedural data,
- Quality of Recovery-15 (QoR-15)

Safety endpoints:

- arterial puncture
- pneumothorax
- hypotension
- arrhythmia
- hypoxia
- airway intervention
- respiratory rate

5 Study Methods

5.1 General Study Design and Plan

The study is an open multicentre randomized controlled trial with a study and a control arm in a 1:1 ratio. Patients will be randomized to either a control arm of LA for SVP-implantation or a study arm of PCS with propofol and alfentanil as adjunct to LA for SVP-implantation. The aim is to randomize 340 patients with an estimated patient recruitment over 18 months with a following 6 months of data cleaning and analysis. The trial will be performed at two centres; County Hospital Ryhov, Jönköping, Sweden and University Hospital Linköping, Sweden. SVP implantation procedure and perioperative time period is estimated to 2-4 hours. The primary endpoint is assessment of patients' self-reported pain perception. Secondary outcomes include patient satisfaction, implantation conditions, sedation level, sedative and analgesic medication consumption, procedural time consumption as well as safety aspects, adverse events and estimation of perioperative experience. Participation in the trial ends after telephone inquiry one day postoperatively.

Control arm:

SVP-implantation in LA:

Subcutaneous venous ports were introduced in 1981. A SVP is a small device around 3cm in diameter with an injectable membrane buried just under the skin. It is connected to a thin tube with its tip in a large bore vein. Access to the SVP is achieved by puncturing the skin with a needle.

Local anaesthetic causes the absence of pain sensation in the location where applied by decreasing the rate of depolarization and repolarization of excitable membranes such as nociceptors and nerves. The most commonly used solutions are from the amide group differing in pharmacokinetics. In order to reduce a burning sensation on infiltration substances can be combined with sodium bicarbonate. There will be no restrictions in the choice of LA-solution being left up to local practice at participating sites. With the beginning of the procedure LA is subcutaneously applied to patients in both groups. LA used at participating centres are Mepivacaine 10mg/ml, 20-40ml subcutaneously or Lidocaine 10mg/ml, 20-40 ml subcutaneously.

Study arm:

SVP-implantation in LA and PCS:

In addition to LA, patients in the study group are able to self-administer a combination of propofol and alfentanil using a patient-controlled sedation pump. The pump enables the patient via a hand-held button to trigger the release of a single bolus of 0.5ml containing 4.5mg propofol and 25µg alfentanil under an 8 second period. This results in a maximal possible amount of 7 bolus doses per minute.

Propofol is a short-acting anaesthetic agent commonly used for general anaesthesia and procedural sedation. Several mechanisms of action have been proposed both through potentiation of GABA_A receptor activity and in higher doses behaving as GABA_A receptor agonist. When used for intravenous sedation a single dose wears off within minutes demanding for continuous or intermittent application.

Alfentanil is a short-acting synthetic opioid analgesic agent with rapid onset of effects at μ -opioid receptors. These properties make it suitable to provide analgesia for brief procedures and to infuse for longer procedures and yet provide relatively rapid recovery.

Rescue sedation will be available to patients in both groups on the patient's or operator's demand. Rescue sedation consists of propofol and alfentanil administered by the clinician and is documented in the e-CRF.

Setting:

This trial will be carried out in the following anaesthesia departments:

OP/IVA-kliniken, County Hospital Ryhov, Sweden

AnOpIVA-kliniken, University Hospital Linköping, Sweden

5.2 Method

Participants will be instructed on use of the PCS pump (Syramed μ SP6000, Arcomed AG, Switzerland) by a nurse anesthetist. The syringe is loaded with 36 ml propofol (10 mg/ml) and 4 ml alfentanil (0.5 mg/ml). Each time the patient presses the handheld button, an aliquot of 0.5 ml is injected (4.5 mg propofol/0.025 mg alfentanil). The injection time is set to 8 s, restricting self-administration to a maximum of 7 bolus doses per minute corresponding to 31.5 mg propofol and 0.175 mg alfentanil per minute. No lockout period is applied. Local anaesthesia is injected in the operating site. Vital parameters prior to the procedure are recorded. Patients are monitored using electrocardiography for heart rate (HR), non-invasive blood pressure (BP), oxygen saturation (SpO₂), and respiratory rate (RR) at 5-min intervals during the procedure. Bradycardia is defined as HR <40 beats/min, tachycardia as HR >100 beats/min, hypotension as systolic BP < 90 mmHg or a decrease of >30% from baseline, hypoxia as SpO₂ <90% or a decrease of >5% from baseline, and bradypnea as RR of <8 breaths per minute. Supplemental oxygen via a capnograph-fitted nasal cannula is administered to all patients at 2 L/min during the procedure. The Observer's Assessment of Alertness/Sedation score (OAA/S) [9] is used to determine the sedation level during the four procedural steps: 1) sterile swabbing, 2) injection of LA, 3) catheter tunneling, and 4) sterile drape removal. The operating anesthesiologist assesses the operating conditions on a 4 point scale with 1 enabling the operator to perform the procedure without time delay and 4 having to abort the procedure. Puncture attempt is defined as continuous needle advancement to establish vein puncture. An unvalidated patient perception assessment tool with seven dimensions applying the NRS is used to evaluate patient perception. QoR-15 will be measured at 3 timepoints. Preoperatively, postoperatively before patient discharge and one day postoperatively.

5.3 Inclusion-Exclusion Criteria and General Study Population

Inclusion criteria:

- Adult patients (≥ 18 years) with cancer scheduled for SVP-implantation at participating anaesthesia departments.

Exclusion criteria:

- Inability to operate the PCS apparatus,
- Inability to communicate in Scandinavian languages.
- Patients who require general anaesthesia or patients eligible for LA only on anesthesiologist's assessment (i.e. severe sleep apnea).
- Propofol or alfentanil allergy. *
- Non-fasting according to guidelines of the Swedish Society for Anaesthesia and Intensive Care (SFAI).
- Failure to achieve peripheral vascular access.
- Pregnancy **
- Previous participation in study

Anaesthesiology assessment will be conducted at the following stages: SVP request, trial inclusion and preoperatively. Assessment includes co-medication assessment.

*According to Summary of Product Characteristics (SmPC) the following is regarded as contraindication:

Propofol: allergy or hypersensitivity against propofol or any of the excipients of the emulsion, Patients who are allergic to peanut or soya.

Alfentanil: hypersensitivity to the active substance, to other opioids, or to any excipients listed under section: List of excipients in SmPC.

**Women in fertile age will be able to participate in the trial after pregnancy testing at the oncology unit before inclusion into the trial (according to Recommendations related to contraception and pregnancy testing in clinical trials).

[figure not shown]
5.4 Enrolment, Flow sheet, Randomization and Blinding

5.4.1 Enrolment

Eligibility for enrolment will be judged by the SVP-scheduling nurse according to inclusion and exclusion criteria. Screening log will be established.

Patients will be given an information sheet about the possibility to participate at the oncology / hematology department prior to SVP booking. On arrival to the preoperative unit a study team member will give full explanation and a physician will be available to answer questions. Signed informed consent is obtained by a physician on the day of the procedure. Inclusion

and randomization and treatment are only applied after the patient not meeting any exclusion criteria. All participants are free to withdraw at any time from the protocol treatment without giving reasons and without prejudicing further treatment (section 5.5).

5.4.2 Randomization

Prior to SVP-implantation and when the patient's eligibility has been confirmed and consent forms have been completed the patient will be randomized by password-coded randomization software accessible to the co-investigators at each participating site (REDCap). All patients must be randomized onto the study prior to SVP-implantation.

Each patient randomized will be allocated a unique sequential patient code number for the randomization arm together with an allocated study arm.

The randomization scheme will be equal allocation (1:1) using an electronic randomization tool. Randomization will be performed consecutively. Patients will not be able to be randomized to the study until all appropriate regulatory requirements have been completed. If a patient withdraws from the trial the unique patient code will not be used again and the patient will not be included into the trial again.

5.5 Withdrawal Criteria

Patients will be informed that they have the right to withdraw from the study at any time for any reason, without prejudice to their medical care. Full details of the reasons for withdrawal will be recorded on the Case Withdrawal Form (CWF) which must be completed if a patient wishes withdrawal from the study and send to the principal investigator. By withdrawal from the study previously collected data remains part of the study database. No subsequent data will be used after withdrawal.

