6.3.3 Intention to Treat Analysis

Analyses will be performed on all participants in the study and control arms respectively which they were randomized to following the intention-to-treat principle.

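### SAP 5.4.1 sends withdrawal from treatment to a rule written for withdrawal from the study, so obtainable outcomes of patients who decline or stop the allocated technique could go unused

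*SAP*

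**What the plan says.** SAP 5.4.1 (Enrolment) states: "All participants are free to withdraw at any time from the protocol treatment without giving reasons". The same sentence ends with a reference to section 5.5.

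SAP 5.5 (Withdrawal Criteria) speaks of a different event. It opens: "Patients will be informed that they have the right to withdraw from the study at any time for any reason". Its form is one "which must be completed if a patient wishes withdrawal from the study". On data it has two rules: "By withdrawal from the study previously collected data remains part of the study database", and then "No subsequent data will be used after withdrawal".

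SAP 6.3.3 sets the analysis principle: "Analyses will be performed on all participants in the study and control arms respectively which they were randomized to following the intention-to-treat principle". Protocol 6.2.3 says the same for the QoR-15 sub-study, and Protocol section 7 makes that population the basis of the analysis.

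On timing, SAP 6.1 has the pain and satisfaction questionnaire filled in before the patient leaves the recovery unit. SAP 5.2 places QoR-15 before the operation, before discharge and one day later.

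**The concern.** Declining or stopping a treatment and leaving a study are different events with different consequences for the data. The SAP names the first, refers it to a section that deals only with the second, and provides no other rule. Staff who follow the reference find an instruction not to use anything collected afterwards.

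The outcomes that matter most come after the point of loss. For a patient handled this way before or during implantation, the primary pain score and two of the three QoR-15 scores would go unused, even if the patient is still in the unit and willing to answer. Staff and patients know the allocation (SAP 5.5.1), and randomisation precedes implantation (SAP 5.4.2). A decision to decline or stop can therefore depend on the arm and on how the procedure is going, and losses of that kind need not be random.

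**Working it through.** **Step 1: the texts side by side.**

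| Question | SAP 5.4.1 | SAP 5.5 |
|---|---|---|
| Withdrawal from what? | the protocol treatment | the study |
| Data already collected | not stated; refers to 5.5 | kept |
| Data collected later | not stated; refers to 5.5 | not used |

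No other section states that follow-up continues after treatment is declined or stopped. The name of the form does not settle the matter: the SAP abbreviation list expands CWF as a consent withdrawal form, while 5.5 calls it a case withdrawal form.

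**Step 2: what would be lost under 5.5.** Kept: the pre-operative QoR-15 and any intraoperative items recorded before withdrawal, such as sedation scores and delivered doses. Not used: the pain questionnaire, the QoR-15 before discharge and the QoR-15 on day 1.

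**Step 3: the plan's own sample size.** Inputs from SAP section 11: 25% with NRS ≥4 in controls, a 50% reduction (so 12.5% with PCS), 80% power, two-sided 5%, 1:1. With mean proportion 0.1875:

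n per arm = [1.960·√(2·0.1875·0.8125) + 0.842·√(0.25·0.75 + 0.125·0.875)]² / 0.125² = 151.9, rounded up to 152.

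This gives 304 in total, against the stated 308, which is close enough to count as reproduced. The 170 per arm corresponds to 154 × 1.10 = 169.4.

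**Step 4: possible distortion of the pain result.** The documents give no rate of declining or stopping, so d and q below are assumptions. Let p be the true PCS-arm rate of NRS ≥4 (0.125), d the share of the PCS arm lost, and q the rate among those lost. Then

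observed rate = (p − d·q) / (1 − d).

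The apparent difference is 25% minus the observed rate; the true difference is 12.5 points.

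| d | q | Observed PCS rate | Apparent difference |
|---|---|---|---|
| 5% | 25% | (0.125 − 0.0125)/0.95 = 11.8% | 13.2 points |
| 5% | 50% | (0.125 − 0.025)/0.95 = 10.5% | 14.5 points |
| 10% | 12.5% | (0.125 − 0.0125)/0.90 = 12.5% | 12.5 points |
| 10% | 25% | (0.125 − 0.025)/0.90 = 11.1% | 13.9 points |
| 10% | 50% | (0.125 − 0.050)/0.90 = 8.3% | 16.7 points |

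If those lost had less pain than the rest of the arm, the shift would reverse: with d = 10% and q = 0, 0.125/0.90 = 13.9%, a difference of 11.1 points. The 50% rows are demanding. At d = 10%, 17 of 170 patients are lost and carry 8.5 of the 0.125 × 170 = 21.25 expected events, or 40% of them.

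**Step 5: power.** With all 340 analysed, power is 84.3% for pain and 82.9% for QoR-15 (difference 6, SD 19, from Protocol section 5). With 10% lost from the PCS arm only, it is 82.1% and 80.9%; with 20% lost, 79.4% and 78.4%. Power changes little, so the issue is which patients are lost.

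**The case against.** The strongest reply is that section 5.5 does not apply to stopping PCS at all. Each of its sentences that names what is withdrawn from names the study, and the bar on later data follows directly from them. The sentence in 5.4.1 sits under Enrolment and can be read as a statement of voluntariness, with the reference pointing to where that right is restated.

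Much of this stands. A reader might infer that any patient who stops pressing the button, or hands it back, loses the pain and QoR-15 scores. The documents do not say so. PCS is used on demand with no minimum use, SAP 11.5 marks treatment compliance as not applicable, and the per-protocol population in SAP 6.3.2 requires only a port and a completed questionnaire. Rescue sedation, general anaesthesia and an aborted procedure are ordinary variables in SAP 5.6, with no link to withdrawal.

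A reader might also infer a flat contradiction with intention to treat. Not using data after a patient has truly left the study creates missing data; it does not by itself breach the principle. The conflict arises only if obtainable outcomes are set aside because treatment was declined or stopped.

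Finally, a reader might infer that the loss must favour PCS because control patients who do poorly can have rescue sedation and stay in. SAP 5.1 offers rescue to both arms, and control patients may withdraw too, so the direction is not established.

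What the reply does not remove is the gap. A patient who formally refuses or ends the allocated technique is given a right in 5.4.1, and the section cited for it has no rule that keeps the later outcomes.

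**Conclusion.** The concern holds as a gap in the rules with a misleading cross-reference. As written, a patient who declines or stops the allocated technique can be handled as a study withdrawal, with loss of the primary pain score and both post-operative QoR-15 scores.

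How often this would happen, and which arm it would favour, cannot be derived from the documents. On the assumed figures above, the shift in the PCS-arm pain rate runs from none to about 4 points (12.5% to 8.3%) at 10% loss, and it could go the other way. The 10% drop-out allowance in SAP section 11 covers the loss of numbers but not selection. The missing-data texts do not close the gap either: SAP 6.5 names an imputation method without describing it, and Protocol 6.3 assumes data missing at random, which is doubtful if stopping reflects discomfort not yet recorded on any score.

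The correction is worth making because it protects the primary endpoint at almost no cost.

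**What to change.** In SAP 5.5, separate two events:

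- (a) **Declining or stopping the allocated technique.** The patient stays in the study, the pain questionnaire and both later QoR-15 forms are still collected, and the patient is analysed as randomised.
- (b) **Withdrawal of consent to further data collection.** Data up to that point are kept and nothing later is used.

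Limit the bar on later data to (b), and correct the cross-reference in 5.4.1 so that treatment withdrawal leads to (a). This concerns data handling only and changes nothing about when or how treatment is stopped.

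The cost is SAP wording and one field on the withdrawal form to record which event occurred. No extra contacts are needed, because the questionnaire and the telephone call are already scheduled for every patient.
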